### 5.1.3 Dose modification and dose delay

Investigators should follow the guidelines *described below* for the modification of LDE225 treatment. Any plan to deviate from these guidelines in view of the patient safety must be previously discussed with Novartis unless there is an urgent need for action.

All dose modifications should be based on the worst preceding toxicity. If study treatment is being held due to toxicity, scheduled visits and all assessments should continue to occur except the dosing of the study drug. Treatment related toxicities are adverse events that are possibly, probably or definitely related to the study drug.

Any grade 3 or grade 4 toxicities will result in discontinuation of the study drug. Men with prolonged grade 2 toxicity will receive a reduced dose of the study drug at 400mg. If the grade 2 toxicitiy continues on the reduced dose then the dose level will be reduced again to 200mg. A maximum of two dose-reduction steps will be allowed (see [Table below](#)), after which the patient will be discontinued from study treatment.

For patients who undergo dose interruptions (delays), if the same toxicity returns after re-initiation of treatment, regardless of duration, the second re-initiation must resume at a lower dose. If the patient requires a dose interruption of >7 days from the previous dose, then the patient must be discontinued from study treatment although he may still undergo prostatectomy. Patients who discontinue the treatment due to an adverse event or an abnormal laboratory value must be followed until resolution or stabilization of the event.

All dose changes or interruptions must be recorded in the dosage administration record (CRF) as appropriate.

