**Table 5-1 Recommended Dose Modifications and Dose Delays for suspected treatment-related toxicities**

Recommended dose modifications for LDE225**	
Worst toxicity CTCAE grade* (value)	During a cycle of therapy
Hematologic	
Neutropenia (ANC)	
Grade 1 (ANC < LLN - 1500/mm  )	Maintain dose level
Grade 2 (ANC < 1500 - 1000/mm  )	Reduce dose to 400mg. If resolved in $\leq$ 7 days then maintain dose level. If not resolved in $\leq$ then decrease level to 200mg
Grade 3 or 4 (ANC < 1000 - 500/mm  or < 500/mm  )	
 
Discontinuation of study drug
 

Thrombocytopenia (PLT)	
Grade 1 (PLT < LLN - 75,000/mm  )	Maintain dose level
Grade 2 (PLT < 75,000 - 50,000/mm  )	Reduce dose to 400mg. If resolved in $\leq$ 7 days then maintain dose level. If not resolved in $\leq$ then decrease level to 200mg
Grade 3 or 4 (PLT < 50,000 - 25,000/mm  or < 25,000/mm  )	
 
Discontinuation of study drug
 

Febrile Neutropenia	
Febrile neutropenia (ANC < $1.0 \times 10^9$ /L, fever $\geq$ 38.5°C)	Omit dose until resolved, then decrease dose by 1 step
Muscle Toxicity	
Elevated creatine phosphokinase (CK)	
Asymptomatic (no new-onset muscle pain/spasm or worsening of pre-existing muscle pain/spasm) CTCAE grade 1 or 2 CK elevation	
 
For CTCAE grade 1 CK elevation, continue treatment on same dose and continue monitoring as per schedule of assessments
 
For sites in France: For treatment-emergent CTCAE grade 1 CK elevation, continue treatment on same dose. CK should be measured weekly until CK returns to normal for baseline value.
 
For CTCAE grade 2 CK elevation, collect blood sample for PK and consider performing a muscle biopsy; continue on same dose level of LDE225. CK should be measured weekly until resolution to <math>\leq</math> grade 1.
 

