Symptomatic (new-onset or worsening of pre-existing muscle pain/spasm) with CTCAE grade 1 or 2 CK elevation	
 
For CTCAE grade 1 CK with muscle pain/spasm <math>\geq</math> CTCAE grade 1, continue treatment at same dose and measure CK weekly until CK returns to normal or baseline value or muscle pain/spasm resolves
 
For CTCAE grade 2 CK with muscle pain/spasm <math>\geq</math> CTCAE grade 1, collect blood sample for PK and continue treatment at same dose level of LDE225. CK should be measured weekly until CK is <math>\leq</math> CTCAE grade 1
 

Recommended dose modifications for LDE225**	
Worst toxicity CTCAE grade* (value)	During a cycle of therapy
CTCAE grade 3 or 4 CK elevation (with or without muscle pain/spasm)	
 
Discontinuation of study drug
 

Muscle pain/spasm (new onset or worsening of pre-existing muscle pain/spasm)	
 
For CTCAE grade 1 muscle pain/spasm, continue treatment on the same dose and planned assessments
 
For CTCAE <math>\geq</math> grade 2 muscle pain/spasm, measure CK weekly until muscle pain resolves to <math>\leq</math> grade 1. If CK is elevated, follow guidance for CK elevation as described above. Continue treatment with LDE225
 
For new-onset CTCAE grade 3 muscle pain/spasm, study drug will be discontinued
 

Renal	
Serum creatinine	
Serum creatinine $<1.5 \times$ ULN	Maintain dose level
Serum creatinine 1.5-3 $\times$ ULN	Omit dose until resolved to $\leq$ grade 1, then: 
 
If resolved in <math>\leq</math> 7 days, then maintain dose level
 
If resolved in <math>></math> 7 days, then decrease dose by 1 step (consider checking serum CK, if not already done)
 

Grade 3 Serum creatinine $> 3.0 - 6.0 \times$ ULN	Discontinuation of study drug
Grade 4 Serum creatinine $> 6.0 \times$ ULN	Discontinuation of study drug
Hepatic	
Bilirubin	
Total bilirubin $<1.5 \times$ ULN	Maintain dose level
Total bilirubin 1.5-3 $\times$ ULN	Omit dose until resolved to $\leq$ grade 1, then: 
 
If resolved in <math>\leq</math> 7 days, then maintain dose level
 
If resolved in <math>></math> 7 days, then decrease by 1 step
 

Grade 3 Total bilirubin $> 3.0 - 10.0 \times$ ULN	Discontinuation of study drug

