Grade 4 Total bilirubin $> 10.0 \times$ ULN	Discontinuation of study drug
AST or ALT	
Grade 1 ( $>$ ULN - 3.0 $\times$ ULN)	Maintain dose level
Grade 2 ( $>$ 3.0 - 5.0 $\times$ ULN)	Maintain dose level
Grade 3 ( $>$ 5.0 - 20.0 $\times$ ULN)	
 
Discontinuation of study drug
 

Grade 4 ( $>$ 20.0 $\times$ ULN)	Discontinuation of study drug

Recommended dose modifications for LDE225**	
Worst toxicity CTCAE grade* (value)	During a cycle of therapy
Cardiac	
Cardiac - prolonged QTc interval ≥ grade 3 (QTc >500 msec or >60 ms from baseline on at least 2 separate ECGs taken within 1 hour)	
First Occurrence:
 
 
• Omit dose
 
• Perform an analysis of serum potassium and magnesium, and if below lower limit of normal, correct with supplements to within normal limits. Concomitant medication usage must be reviewed.
 
• Perform a repeat ECG within one hour of the first QTc >500 ms
 
• If QTc remains > 500 ms, repeat ECG as clinically indicated but at least once a day until the QTc returns to <480 ms.
 
• Once QTc prolongation has resolved, study treatment may be restarted at a reduced dose level
 
 
Second Occurrence:
 
 
• discontinue patient from further study treatment
 

Cardiac, general	
Grade 1 or 2	Maintain dose level
Grade 3	Discontinuation of study drug
Grade 4	Discontinuation of study drug
Other adverse events**	
Grade 1 or 2	Maintain dose level
Grade 3	Discontinuation of study drug
Grade 4	Discontinuation of study drug
All dose modifications should be based on the worst preceding toxicity. Treatment related toxicities are adverse events that are possibly, probably or definitely related to the study drug.	
If the dose-limiting toxicity recurs in a patient following 2 dose reductions, then further therapy with LDE225 will not be continued.	
If a patient requires a dose interruption of > 21 days from the intended day of the next scheduled dose because of an LDE225-related toxicity, then the patient must be discontinued from the study.	
*Common Toxicity Criteria for Adverse Events (CTCAE Version 4.0).	

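### Section 5.1.3 stops LDE225 for good in situations where Table 5-1 orders a restart at a lower dose, and no text says which governs

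*Combined protocol and SAP*

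**What the plan says.** Section 5.1.3 sets two stopping rules without exceptions. On interruptions: "If the patient requires a dose interruption of >7 days from the previous dose, then the patient must be discontinued from study treatment". The same sentence lets the man go on to prostatectomy. On severity: "Any grade 3 or grade 4 toxicities will result in discontinuation of the study drug".

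Table 5-1, which follows, gives instructions by toxicity.

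- **Creatinine 1.5 to 3 x ULN.** Hold until grade 1 or better. If that takes longer than a week, the line reads "7 days, then decrease dose by 1 step (consider checking serum CK, if not already done".
- **Bilirubin 1.5 to 3 x ULN.** Same structure: "7 days, then decrease by 1 step".
- **Febrile neutropenia, ANC below 1.0 x 10^9/L.** "Omit dose until resolved, then decrease dose by 1 step".
- **Neutropenia.** The row beginning "Grade 3 or 4 (ANC < 1000 - 500/mm" calls for discontinuation.
- **First QTc prolongation of grade 3 or more.** "Once QTc prolongation has resolved, study treatment may be restarted at a reduced dose level". Only a second occurrence requires stopping.
- **Closing note.** A related interruption of more than 21 days, counted from the intended day of the next dose, takes the patient off the study.

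Just before the table, 5.1.3 sends the reader for detail by type and severity to a Table 5-3. The documents contain no table of that number; the one that follows is numbered 5-1.

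**The concern.** For a long creatinine or bilirubin hold, and for febrile neutropenia, one text orders a permanent stop and the other orders re-dosing. An investigator cannot obey both. Two careful investigators could treat the same patient in opposite ways, each citing the protocol.

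What is at stake is mainly safety: whether a man awaiting potentially curative surgery is re-exposed to a drug that has just caused a toxicity. A smaller matter is that the plan does not fix how much drug he takes before the prostatectomy specimen used for the *Gli1* endpoint. The 21-day note raises a further question, whether a man who stops drug still contributes that specimen. Each man is 1/11, about 9%, of the treated arm.

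**Working it through.** The plan gives no figure to reproduce here. The check sets the texts side by side and then sizes the effect.

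**1. The texts compared**

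| Situation | Section 5.1.3 | Table 5-1 | Can both be followed? |
|---|---|---|---|
| Creatinine or bilirubin 1.5-3 x ULN, resolved in >7 days | Stop drug | Restart one step lower | No |
| Febrile neutropenia, ANC <1.0 x 10^9/L | Stop drug (grade 3/4) | Restart one step lower | No |
| First QTc prolongation, grade 3 or more | Stop drug | Restart permitted | Yes, by stopping |
| Length of interruption | >7 days: off drug, surgery still allowed | >21 days: off study | Limit and consequence differ |

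For neutropenia, 1.0 x 10^9/L equals 1000/mm^3, so the febrile row covers the counts that the table's own neutropenia row grades 3 or 4 and discontinues. Read literally, a man at that count without fever stops for good, while a man at the same count with fever restarts.

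**2. Does the creatinine/bilirubin conflict depend on how days are counted?** Take labs on Day 14 and the last dose on Day 13. Resolution in more than 7 days means Day 22 at the earliest.

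- Missed doses: Days 14 to 21, which is 8.
- Days from the previous dose: 22 - 13 = 9.

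Both exceed 7, so the conflict stands on either count.

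**3. Can the 21-day limit be reached?** Surgery is on Day 28 +/- 3, so Day 31 at the latest. To exceed 21 days by then, the first missed dose must fall on or before Day 31 - 22 = Day 9, ahead of the first scheduled on-treatment labs. Inside the surgical window the note has almost no scope.

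**4. Drug in dispute, creatinine or bilirubin hold found on Day 14.** The earliest disputed dose is on Day 22. Assume the last dose is the day before surgery.

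- Surgery Day 25: Days 22-24, 3 doses; 3 x 400 mg = 1.2 g of 24 x 800 mg = 19.2 g, or 6%.
- Surgery Day 31: Days 22-30, 9 doses; 9 x 400 mg = 3.6 g of 30 x 800 mg = 24 g, or 15%.
- Resolution seen only at the next scheduled labs, on the day of surgery: 0 doses.

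Any figure above zero needs unscheduled labs. The median effective half-life of 19 days (Section 1.4.2) softens the effect further. The febrile neutropenia and QTc rows set no minimum hold, so a short hold there would leave more doses; 15% is the ceiling for the laboratory rows only.

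**5. How often?** With per-patient risk p, P(at least one in 11) = 1 - (1 - p)^11.

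- *Febrile neutropenia, QTc.* Section 1.4.1 reports no related, clinically significant hematology or ECG change in 103 patients. Read as 0/103, the one-sided 95% upper limit is 1 - 0.05^(1/103) = 2.9%, giving at most 27%. With only the 26 patients at 800 mg, the limit is 1 - 0.05^(1/26) = 10.9%, giving 1 - 0.05^(11/26) = 72%, which mainly reflects the small denominator.
- *Creatinine, bilirubin.* Neither appears in Table 1-2, which lists events in 5% or more of patients, so each is at most 5/103 = 4.9%. Assume that 25% to 100% of events need a hold longer than 7 days. Then, for each test, the chance is 13% to 42% at 5/103 and 3% to 10% at 1/103. The 42% is a ceiling: it takes the highest unlisted rate, counts all grades and assumes every event needs a long hold. In the other direction, entry is allowed up to 1.5 x ULN for both tests, where the hold band begins.

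**The case against.** The best defence is that a specific row overrides a general rule, since 5.1.3 refers the reader to the table for detail by type and severity. That is a fair inference, but it remains an inference. The reference cites a table number that does not exist and never says the table prevails. The table is headed as recommended, whereas 5.1.3 is worded as mandatory. Letting the table govern would also keep the neutropenia anomaly, where fever leads to the milder instruction.

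A second defence is that 5.1.3 requires any planned deviation from the guidelines to be discussed beforehand with the drug supplier unless action is urgent, and a table footnote offers case-by-case discussion. This is a real safeguard and makes an unconsidered restart less likely. It sets no default, however, and a site must first know which text it would be deviating from.

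Third, the trial is small, with biopsy and specimen work at one institution, and surgery can proceed after drug is stopped. That bears on severity and is accepted.

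Two stronger readings are tempting, and the documents do not support them.

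- *Grade 2 CK as a further conflict.* Section 5.1.3 says "Men with prolonged grade 2 toxicity will receive a reduced dose of the study drug at 400mg", while the CK rows keep the same dose. But in those rows the time limit of grade 1 or better attaches to the weekly CK test and not to the dose. They can be read with 5.1.3 as keeping the dose unless the event becomes prolonged, just like the AST/ALT rows. What remains is that prolonged is undefined. Table 1-2 pools grades 1 and 2 (6 of 26 at 800 mg) and gives no duration, so the frequency of prolonged grade 2 CK cannot be derived.
- *The table's line for resolution within 7 days as a conflict too.* With the last dose on Day 13 and restart on Day 21, the gap is 8 days from the last dose but only 7 doses are missed (Days 14 to 20). Whether 5.1.3 stops drug depends on how an interruption is counted. That supports stating one clock and does not establish a contradiction.

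**Conclusion.** The point holds as an internal inconsistency. For creatinine or bilirubin holds longer than 7 days, and for febrile neutropenia, the protocol gives opposing orders and no rule for choosing between them. The 21-day note conflicts with 5.1.3 in both limit and consequence. The QTc row is a lesser inconsistency.

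A reader might infer that this endangers the *Gli1* comparison. The figures do not show that. For a laboratory hold found on Day 14, the disputed drug is 0 to 9 doses of 400 mg, at most 15% of planned dose, and the upper figure needs unscheduled labs and the latest surgery date. The events are probably infrequent, although the upper limits are loose. The likelihoods rest on reading the phase I statement as zero events, on carrying over rates from patients with advanced solid tumors at mixed doses, and on an assumed share of long holds.

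The case therefore rests on the clarity of a safety instruction. It should be fixed, at the low end of that category.

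**What to change.** Amend the wording as follows.

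1. State in 5.1.3 that its rules govern over Table 5-1. Adopting the table rows as named exceptions would also remove the ambiguity, but the stricter text suits a 4-week course before surgery.
2. In the creatinine and bilirubin rows, replace the lines that reduce the dose after more than 7 days with discontinuation. Use one clock throughout, days from the last dose taken: restart only if the next dose falls within 7 days of it (last dose Day 13, restart by Day 20).
3. Change febrile neutropenia to discontinuation.
4. Change the first-occurrence QTc instruction to discontinuation, or name it in 5.1.3 as an exception.
5. Delete the 21-day note, or align it with the 7-day rule so that a man who stops drug stays in the study for prostatectomy.
6. Correct the reference to Table 5-3 so that it reads Table 5-1.
7. Optionally, define prolonged grade 2 toxicity, for example as more than 7 days, the period the table already uses.

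This adds no scheduled assessments. The cost is slightly more permanent drug stops, and so somewhat lower exposure in the few men affected.

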**Table Dose reductions for LDE225**

Dose reduction*			
	Starting dose level	Dose level -1	Dose level -2
LDE225 dose (mg QD)	800	400	200

\*Dose reduction should be based on the worst toxicity demonstrated.

Detailed indications and instructions for dose-modifications are shown below in Table 5-3. Different dose modifications are dependent on the type and severity of the toxicity, as shown in Table 5-3.

**Table 5-1 Recommended Dose Modifications and Dose Delays for suspected treatment-related toxicities**

Recommended dose modifications for LDE225**	
Worst toxicity CTCAE grade* (value)	During a cycle of therapy
Hematologic	
Neutropenia (ANC)	
Grade 1 (ANC < LLN - 1500/mm  )	Maintain dose level
Grade 2 (ANC < 1500 - 1000/mm  )	Reduce dose to 400mg. If resolved in $\leq$ 7 days then maintain dose level. If not resolved in $\leq$ then decrease level to 200mg
Grade 3 or 4 (ANC < 1000 - 500/mm  or < 500/mm  )	
 
Discontinuation of study drug
 

Thrombocytopenia (PLT)	
Grade 1 (PLT < LLN - 75,000/mm  )	Maintain dose level
Grade 2 (PLT < 75,000 - 50,000/mm  )	Reduce dose to 400mg. If resolved in $\leq$ 7 days then maintain dose level. If not resolved in $\leq$ then decrease level to 200mg
Grade 3 or 4 (PLT < 50,000 - 25,000/mm  or < 25,000/mm  )	
 
Discontinuation of study drug
 

Febrile Neutropenia	
Febrile neutropenia (ANC < $1.0 \times 10^9$ /L, fever $\geq$ 38.5°C)	Omit dose until resolved, then decrease dose by 1 step
Muscle Toxicity	
Elevated creatine phosphokinase (CK)	
Asymptomatic (no new-onset muscle pain/spasm or worsening of pre-existing muscle pain/spasm) CTCAE grade 1 or 2 CK elevation	
 
For CTCAE grade 1 CK elevation, continue treatment on same dose and continue monitoring as per schedule of assessments
 
For sites in France: For treatment-emergent CTCAE grade 1 CK elevation, continue treatment on same dose. CK should be measured weekly until CK returns to normal for baseline value.
 
For CTCAE grade 2 CK elevation, collect blood sample for PK and consider performing a muscle biopsy; continue on same dose level of LDE225. CK should be measured weekly until resolution to <math>\leq</math> grade 1.
 

Symptomatic (new-onset or worsening of pre-existing muscle pain/spasm) with CTCAE grade 1 or 2 CK elevation	
 
For CTCAE grade 1 CK with muscle pain/spasm <math>\geq</math> CTCAE grade 1, continue treatment at same dose and measure CK weekly until CK returns to normal or baseline value or muscle pain/spasm resolves
 
For CTCAE grade 2 CK with muscle pain/spasm <math>\geq</math> CTCAE grade 1, collect blood sample for PK and continue treatment at same dose level of LDE225. CK should be measured weekly until CK is <math>\leq</math> CTCAE grade 1
 

Recommended dose modifications for LDE225**	
Worst toxicity CTCAE grade* (value)	During a cycle of therapy
CTCAE grade 3 or 4 CK elevation (with or without muscle pain/spasm)	
 
Discontinuation of study drug
 

Muscle pain/spasm (new onset or worsening of pre-existing muscle pain/spasm)	
 
For CTCAE grade 1 muscle pain/spasm, continue treatment on the same dose and planned assessments
 
For CTCAE <math>\geq</math> grade 2 muscle pain/spasm, measure CK weekly until muscle pain resolves to <math>\leq</math> grade 1. If CK is elevated, follow guidance for CK elevation as described above. Continue treatment with LDE225
 
For new-onset CTCAE grade 3 muscle pain/spasm, study drug will be discontinued
 

Renal	
Serum creatinine	
Serum creatinine $<1.5 \times$ ULN	Maintain dose level
Serum creatinine 1.5-3 $\times$ ULN	Omit dose until resolved to $\leq$ grade 1, then: 
 
If resolved in <math>\leq</math> 7 days, then maintain dose level
 
If resolved in <math>></math> 7 days, then decrease dose by 1 step (consider checking serum CK, if not already done)
 

Grade 3 Serum creatinine $> 3.0 - 6.0 \times$ ULN	Discontinuation of study drug
Grade 4 Serum creatinine $> 6.0 \times$ ULN	Discontinuation of study drug
Hepatic	
Bilirubin	
Total bilirubin $<1.5 \times$ ULN	Maintain dose level
Total bilirubin 1.5-3 $\times$ ULN	Omit dose until resolved to $\leq$ grade 1, then: 
 
If resolved in <math>\leq</math> 7 days, then maintain dose level
 
If resolved in <math>></math> 7 days, then decrease by 1 step
 

Grade 3 Total bilirubin $> 3.0 - 10.0 \times$ ULN	Discontinuation of study drug
Grade 4 Total bilirubin $> 10.0 \times$ ULN	Discontinuation of study drug
AST or ALT	
Grade 1 ( $>$ ULN - 3.0 $\times$ ULN)	Maintain dose level
Grade 2 ( $>$ 3.0 - 5.0 $\times$ ULN)	Maintain dose level
Grade 3 ( $>$ 5.0 - 20.0 $\times$ ULN)	
 
Discontinuation of study drug
 

Grade 4 ( $>$ 20.0 $\times$ ULN)	Discontinuation of study drug

Recommended dose modifications for LDE225**	
Worst toxicity CTCAE grade* (value)	During a cycle of therapy
Cardiac	
Cardiac - prolonged QTc interval ≥ grade 3 (QTc >500 msec or >60 ms from baseline on at least 2 separate ECGs taken within 1 hour)	
First Occurrence:
 
 
• Omit dose
 
• Perform an analysis of serum potassium and magnesium, and if below lower limit of normal, correct with supplements to within normal limits. Concomitant medication usage must be reviewed.
 
• Perform a repeat ECG within one hour of the first QTc >500 ms
 
• If QTc remains > 500 ms, repeat ECG as clinically indicated but at least once a day until the QTc returns to <480 ms.
 
• Once QTc prolongation has resolved, study treatment may be restarted at a reduced dose level
 
 
Second Occurrence:
 
 
• discontinue patient from further study treatment
 

Cardiac, general	
Grade 1 or 2	Maintain dose level
Grade 3	Discontinuation of study drug
Grade 4	Discontinuation of study drug
Other adverse events**	
Grade 1 or 2	Maintain dose level
Grade 3	Discontinuation of study drug
Grade 4	Discontinuation of study drug
All dose modifications should be based on the worst preceding toxicity. Treatment related toxicities are adverse events that are possibly, probably or definitely related to the study drug.	
If the dose-limiting toxicity recurs in a patient following 2 dose reductions, then further therapy with LDE225 will not be continued.	
If a patient requires a dose interruption of > 21 days from the intended day of the next scheduled dose because of an LDE225-related toxicity, then the patient must be discontinued from the study.	
*Common Toxicity Criteria for Adverse Events (CTCAE Version 4.0).	
** If the investigator deems that a recommended dose reduction or the recommendation to maintain the same dose level is not in the best interest of the patient, this decision may be discussed with Novartis on a case-by-case basis.	

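### Table 5-1 continues LDE225 in two places for grade 3 muscle pain/spasm with CK below grade 3, where Section 5.1.3 stops it, and no text says which prevails

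*Combined protocol and SAP*

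**What the plan says.** The body text of Section 5.1.3 gives a general rule: "Any grade 3 or grade 4 toxicities will result in discontinuation of the study drug". It states no exception for muscle symptoms.

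Table 5-1, in the same section, has three muscle entries that matter here.

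- **Muscle pain/spasm row.** Its label is "Muscle pain/spasm (new onset or worsening of pre-existing muscle pain/spasm"), so it covers both new pain and old pain that has got worse. The second bullet applies from grade 2 upward. It asks for weekly CK and ends "If CK is elevated, follow guidance for CK elevation as described above. Continue treatment with LDE225". The third bullet reads "For new-onset CTCAE grade 3 muscle pain/spasm, study drug will be discontinued".
- **Symptomatic CK grade 1 or 2 row.** This also covers new and worsening pain. For CK grade 1 the instruction applies to pain at or above "CTCAE grade 1, continue treatment at same dose and measure CK weekly until CK returns to normal or baseline value", or until the pain resolves. For CK grade 2 it applies to pain at or above "CTCAE grade 1, collect blood sample for PK and continue treatment at same dose level of LDE225".
- **CK grade 3 or 4 row.** For "CTCAE grade 3 or 4 CK elevation (with or without muscle pain/spasm") the drug is discontinued.

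A footnote to the table says that an investigator who thinks a recommended reduction, or a recommendation to keep the dose, is wrong for the patient may discuss the case with the drug supplier.

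**The concern.** The section and its table should give one answer for one patient. For some men with grade 3 muscle pain they give two. An investigator working from the table row could keep such a man on LDE225 in the weeks before radical prostatectomy, while one working from the body text would stop it.

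Muscle effects are prominent with this drug. At 800 mg once daily, Table 1-2 lists grade 1/2 muscle spasms in 9 of 26 patients and grade 1/2 myalgia in 5 of 26, so these rows will be consulted even if grade 3 pain is seldom seen. What is at stake is the handling of an individual patient and consistency between investigators.

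**Working it through.** The plan states no figure on this point. The check is to trace each case of suspected drug-related grade 3 pain/spasm through the three instructions.

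| Grade 3 pain/spasm | CK | 5.1.3 text | Pain/spasm row | CK rows | Result |
|---|---|---|---|---|---|
| Worsening of pre-existing | Normal | Stop | Continue (bullet 2) | Not applicable | Conflict with 5.1.3 |
| Worsening of pre-existing | Grade 1 or 2 | Stop | Continue (bullet 2) | Continue, same dose | Conflict with 5.1.3, in both rows |
| New onset | Normal | Stop | Stop (bullet 3) | Not applicable | Consistent |
| New onset | Grade 1 or 2 | Stop | Stop (bullet 3) | Continue, same dose | CK row conflicts with 5.1.3 and with bullet 3 |
| Either | Grade 3 or 4 | Stop | Bullet 2 refers to CK guidance | Stop | Consistent |

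**Reading of bullet 3.** Its wording could mean any pain that newly reaches grade 3. That is less natural, because the row label and the symptomatic CK row both treat new onset and worsening as separate categories. If it is accepted, the first line of the table becomes consistent. The second and fourth lines still conflict, because the symptomatic CK row has no ceiling.

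**Search for a ranking rule.** Four places might settle the matter, and none does.

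1. Section 5.1.3 sends the reader to the table for detail (calling it Table 5-3), but does not say that the table overrides the text.
2. Section 5.1.3 requires prior discussion with the drug supplier before departing from the guidelines, except in urgent need. That does not rank one part of the guidelines above another.
3. The instruction to act on the worst preceding toxicity tells the reader which grade to use, not which instruction to follow.
4. The table's discretion footnote allows a case-by-case discussion and goes no further.

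The table's row for other adverse events stops the drug at grade 3, but muscle pain has its own row and does not fall there.

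**Frequency.** From Table 1-2, reading blank cells as zero:

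- Grade 3/4 myalgia, all doses: 1/103 = 1.0%. The exact 95% interval is 0.02% to 5.3%; its lower limit is 1 − 0.975^(1/103) = 0.0002, and its upper limit is the 0.975 quantile of Beta(2, 102) = 0.0529.
- Grade 3/4 myalgia, 800 mg once daily: 0/26. The exact 95% upper limit is 1 − 0.025^(1/26) = 0.132, or 13.2%.
- Grade 3/4 muscle spasm: none listed at any dose.

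The documents do not say how many such events were worsening of earlier pain, or what the CK grade was at the time. I therefore give no probability for the 11 men planned for the LDE225 arm.

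**The case against.** The best defence is that the context points to stopping. Section 5.1.3 is mandatory in tone, while the table's title calls its contents recommended. Almost every other row stops the drug at grade 3: neutropenia, thrombocytopenia, CK, creatinine, bilirubin, AST/ALT, general cardiac and other events. Bullet 2 cannot be wholly unlimited either, since new-onset grade 3 pain meets both bullets and bullet 3 must win. A grade 3 cut-off is thus already present, and only its reach is in doubt. All of this stands as evidence of the likely intent. It does not put a ceiling on the symptomatic CK row, and it is not a stated rule.

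One could argue the reverse, that an organ-specific exception was meant. Febrile neutropenia (whose neutrophil limit is grade 3 or 4 in the same table) and QTc prolongation of grade 3 or higher both depart from 5.1.3. But those rows spell out what to do: hold the dose, then resume at a lower one. Grade 3 muscle pain reaches a continue instruction only because no upper limit was written.

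The discretion footnote also counts. A reader might infer that the protocol obliges the investigator to dose through grade 3 pain. It does not: the footnote opens a maintain-dose recommendation to discussion, and 5.1.3 allows urgent action on safety grounds. This softens the conflict without resolving it.

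A reader might also set the second bullet against the 5.1.3 rule "Men with prolonged grade 2 toxicity will receive a reduced dose of the study drug at 400mg". I do not press that. The bullet says to continue, not to continue at the same dose, so a reduction remains compatible with it. Other rows (AST/ALT, general cardiac, other events) also keep the dose at grade 2, so this would not be a fault particular to muscle pain.

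**Conclusion.** The inconsistency is real and minor. It arises only with CK below grade 3. The symptomatic CK row conflicts with 5.1.3 on either reading of bullet 3, for new and worsening pain alike. The conflict within the pain/spasm row rests on reading new onset as distinct from worsening, which I think is the more natural reading but not the only one.

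Few patients should be affected. Section 4.2 excludes men with neuromuscular or muscular disorders, Section 4.1 requires CK below 1.5 × ULN where known, and Section 3.1.3 limits treatment to 4 weeks (± 3 days). The 800 mg data are too sparse to bound the rate usefully.

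It would be tempting to infer damage to the trial's results or its safety oversight. The documents do not support that. Little effect on the Gli1 comparison is expected from so rare an event, and a drug-related grade 3 event counts toward the closure rule in Section 5.1.4 whether or not dosing continues.

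**What to change.** Make four wording changes at the next amendment.

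1. In the muscle pain/spasm row, limit bullet 2 to grade 2.
2. Reword bullet 3 as: *grade 3 or higher muscle pain/spasm, new-onset or worsening of pre-existing: discontinue study drug*. Adding *or higher* keeps grade 4, which bullet 3 does not now name, from being left without a stop instruction.
3. Cap the symptomatic CK grade 1-2 row at pain/spasm of grade 1-2.
4. Add one sentence to 5.1.3: its grade 3/4 discontinuation rule prevails over Table 5-1 except where a row states an explicit exception, namely febrile neutropenia and a first QTc occurrence.

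The cost is edits to two table rows and one added sentence. Sample size, visits and analysis stay as they are.
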